Protocol version 1.4

29 July 2021

Statistical Analysis Plan (SAP)

Double-Blind Cluster Randomised Controlled Trial of Chicken Liver and Eggshell Crackers in Pregnant and Lactating Mothers in a Disadvantaged Setting in Indonesia in 2021

GENERAL INFORMATION

Research Project : *Wellcome Trust Grant - 216447/Z/19/Z*

Intervention Product Identity : UNS84605 (MEC (*micronutrient-enriched crackers*) and Placebo)

Title : Double-Blind Cluster Randomised Controlled Trial of Chicken Liver and Eggshell Crackers in Pregnant and Lactating Mothers in a Disadvantaged Setting in Indonesia in 2021

Principal Investigator : dr. [name], M.Kes, MPH (Nutr), Ph.D.

Institution

Name : Southeast Asian Ministers of Education Regional Centre for Food and Nutrition (SEAMEO RECFON)

Address : [name]

Telephone/Fax : [contact]/ [contact]

ClinicalTrials.gov identifier : NCT04564222

Version : 1.4

Date : 29 July, 2021

Table of Contents

GENERAL INFORMATION	1
1. Introduction	3
2. Study design	3
2.1 Brief Description.....	3
2.2 Place and Time.....	4
2.3 Intervention Product.....	4
2.4 Population and Sample	5
2.4.1 Inclusion and Exclusion Criteria.....	5
2.4.2 Population and Sample size calculation.....	8
3. Study Goals and Objectives.....	10
3.1 Study Goals.....	10
3.2 Secondary Outcomes	10
4. Data Management and Analyses	11
4.1 Data Management	11
4.2 Statistical Analysis.....	11

1. Introduction

The objective of this project is to conduct a Double-Blind Cluster Randomised Clinical Trial (RCT) to assess the impact of daily maternal consumption of MEC on infant birth length and linear growth. Previous interventions have primarily focused on birth weight. This Statistical Analysis Plan (SAP) aims to offer a comprehensive description of the study endpoints and the corresponding analysis methods.

2. Study design

2.1 Brief Description

The design of this study is a double-blind two-phase cluster randomized controlled trial to examine the effect of daily consumption of locally produced MEC (intervention group) compared to placebo crackers (control groups) in two time intervals: 1) from the second trimester of pregnancy (8-14 weeks) to delivery only; and 2) when the intervention is continued for up to 5 months post-partum, with the primary outcomes being birth length, attained linear growth, and growth velocity of the infant.

A total of 28 clusters (villages) will be randomised to either intervention or control using a randomized sequence. Selected pregnant women from these villages will receive daily interventions in the form of 7 x 75 gram micronutrient-enriched food products, made from basic ingredients of liver and chicken eggshells (Micronutrient-enriched Crackers/MEC) or placebo. The research team will give 100 grams of the same product as the respondents to the family of the respondents, so the respondents will not need to share the intervention product with the other family members. MEC or placebo will be produced locally and be identical in size, color, and packaging. MEC or placebo packages will be coded and only the production manager will know the allocated codes for the MEC or placebo packages. The production manager will be instructed to not share the code with any of the investigators involved in the trial until the primary outcomes of the study have been analyzed statistically or as requested by the Ethics Committee and/or Data Safety Monitoring Board (DSMB).

2.2 Place and Time

This study will include 28 villages (Table 2) in 3 subdistricts, namely Tanjungsari, Pamulihan, and Sukasari, in Sumedang District, West Java. The timing of the research will be from July 2020 - July 2023.

2.3 Intervention Product

This study will use micronutrient-enriched crackers (MEC) and placebo as the intervention products. The intervention products are made from the ingredients that can be seen in Table 1.

Table 1. MEC and Placebo Recipes

MEC			Placebo		
Ingredient	Weight (g)	Percentage (%)	Ingredient	Weight (g)	Percentage (%)
Tapioca flour	47	8.6	Tapioca flour	40	9.4
Chicken liver	160	29.3	MOCAF	35	8.2
Drinking water	10	1.8	Drinking water	38	8.9
Wheat flour	200	36.6	Wheat flour	165	38.8
Salt	3	0.5	Salt	2	0.5
Garlic	18	3.3	Garlic	18	4.2
Mushroom bouillon powder	4	0.7	Chicken stock powder	4	0.9
Margarine	50	9.2	Margarine	40	9.4
Chicken egg	30	5.5	Chicken egg	30	7.1
Green onion	15	2.7	Green onion	15	3.5
Coriander leaf	23	4.2	Celery	23	5.4
Eggshell powder	8	1.5	Pangium edule dried seed	15	3.5
Bay leaf	1	0.2	Dough weight	425	100
Ginger	1	0.2	Cooked weight	300	-
Lemon juice	2	0.4			
Lemongrass	2	0.4			
Alpinia galangal	1	0.2			
Lime leaf	1	0.2			
Dough weight	546	100			
Cooked weight	450	-			

2.4 Population and Sample

2.4.1 Inclusion and Exclusion Criteria

1) Inclusion Criteria

- a. Pregnant women aged 19-35 years old;
- b. Gestational age 7-13 weeks at the time of the screening process and be willing to take part in an intervention study at 8-14 weeks gestation;
- c. Permanent residents who will stay in the research area for the following 1 year.

2) Exclusion Criteria

- a. Mothers who have chronic diseases such as hypertension (blood pressure \geq 140/90 mmHg) or under treatment for hypertension, diabetes (non-fasting blood sugar when >200 mg/dL) or under treatment for diabetes, hypercholesterolemia (blood total cholesterol >240 mg/dL), hyperuricemia (blood uric acid > 6 mg/dL), have had a history of tuberculosis or under treatment for tuberculosis or under treatment for other chronic diseases that requires a long treatment, such as cancer, heart disease, epilepsy, etc.;
- b. Have a history of preeclampsia/eclampsia and gestational diabetes in their previous pregnancy;
- c. Have a risk of chronic energy deficiency (mid-upper arm circumference < 23.5 cm);
- d. Have severe anemia (hemoglobin < 70 g/L);
- e. Have a history of allergy to chicken liver and/or eggs.

3) Drop-out criteria

- a. Preeclampsia, eclampsia;
- b. Dead infant/stillbirth;
- c. Twin delivery;
- d. Infants are born with congenital anomalies;
- e. Infants are not breastfed.

4) Other criteria

If an infant is born with Low Birth Weight (LBW) or is premature, then the infant will not be included in the measurement of breast milk volume and

assessment of exclusive breastfeeding status with Deuterium Oxide Dose-to-Mother Technique. However, the growth and data collection such as anthropometry and ages and stages questionnaires (ASQ-3) will still be carried out.

[figure not shown]

Figure 1 Study designs. MEC: Micronutrient-enriched Crackers.

2.4.2 Population and Sample size calculation

The population of this study are the people who live in the area of Pamulihan, Sukasari and Tanjungsari Sub-Districts, Sumedang District, West Java. All parameters used in calculating sample sizes can be seen in Table 1. Design effects, cluster/village, are estimated using previous data collected in the same area.

- 1) Phase 1: To detect a 1 cm difference in birth length between the intervention and control groups (this is approximately 0.5 SD from the WHO Growth Chart (2007)), with power of 0.90, statistical significance of 0.05, and design effect of 1.1 due to village clusters, a minimum sample size of 228 is required (114 in each group) (to be presented in tabular form).
- 2) Phase 2: Based on an average growth velocity of 3-3.2 cm/month, and to detect differences in growth velocity of 0.70 cm between the intervention and control groups, with power of 0.80, statistical significance of 0.05, assuming a standard deviation of 2.2 cm/month, a within-person correlation of 0.73 and a design effect of 1.1 due to village clusters, a sample size of 162 would be required (81 in each group) (to be presented in tabular form).

As the primary outcomes for Phase 1 require a sample size of 228, then 11 participants from 22 clusters will be required. However, we aim to recruit 11 participants from 28 clusters, giving a sample size of 308. This will allow for exclusion due to stillborn or premature birth (~10%, i.e., n~15 in each group) and drop-out or loss-to-follow-up of approximately 15%, so the total sample size is 324. For Phase 2, if 231 participants are retained, a further 1-5% may fail to breastfeed their infants, giving a final sample size of 219-228 to assess Phase 2 outcomes. This sample size will also permit the detection of the differences in the secondary outcomes also specified below (Table 2), in addition to the primary outcomes.

Table 2. Parameters used in calculating sample sizes for secondary outcomes

Measure	Observed mean	Observed SD	Difference to detect	ICC	Design effect	Sample size**
Birth length (cm) ^a	49.7	2.2	1.0	0.010	1.10	114
Infant length at 5 months (cm) ^a	63.0	2.2	1.0	0.010	1.10	114
Birth weight (g) ^a	3013	514	200	0.010	1.10	116
Haemoglobin at 3 rd trimester (g/dL) ^b	12.6	1.2	0.5	0.048	1.48	132
Volume of breast milk at 5 months post-partum (mL/day) ^c	787	148	70	0.010	1.10	80
Micronutrient concentrations of breast milk at 5 months post-partum (Vit A, µg/L) ^c	634	281	130	0.036	1.36	102
Maternal diet at 5 months post-partum (Vit A, µg RAE/d) ^d	478	244	110	0.010	1.10	87
Maternal micronutrient status at 5 months post-partum (Ferritin, µg/L) ^e	35.8	29.7	13.0	0.010	1.10	91
Infant micronutrient status at aged 5 months (Ferritin, µg/L) ^e	46.7	35.6	15.0	0.010	1.10	99

*ICC: intra-class correlation

*Design effect: based on the average size of cluster= 11

**Required sample size per group with 80% power and alpha= 0.05

^aData from observation by Diana A, Mallard SR, Haszard JJ, Purnamasari DM, Nurulazmi I, Herliani PD, et al. Consumption of fortified infant foods reduces dietary diversity but has a positive effect on subsequent growth in infants from Sumedang district, Indonesia. PLoS One. 2017 Apr; 12(4):1-17;

^bData from observation by Diana A, Haszard JJ, Purnamasari DM, Nurulazmi I, Luftimas DE, Rahmannia S, et al. Iron, zinc, vitamin A, and selenium status in a cohort of Indonesian infants after adjusting for inflammation using several different approaches. Br J Nutr. 2017 Nov; 118(10):830-839;

^cData from observation by Daniels L, Gibson RS, Diana A, Haszard JJ, Rahmannia S, Luftimas DE, et al. Micronutrient intakes of lactating mothers and their association with breastmilk concentrations and micronutrient adequacy of exclusively breastfed Indonesian infants. Am J Clin Nutr. 2019 Aug; 110(2):391-400;

^dData from observation by Rahmannia S, Diana A, Luftimas DE, Gurnida DA, Herawati DMD, Houghton LA, et al. Poor dietary diversity and low adequacy of micronutrient intakes among rural Indonesian lactating women from Sumedang district, West Java. PLoS One. 2019 Jul; 14(7):1-13;

^eUnpublished data

3. Study Goals and Objectives

This will be the first RCT in Indonesia to examine the effect of daily maternal consumption of MEC on birth length and infant linear growth; earlier interventions have examined only birth weight.

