3.1 Study Goals

- 1) To determine whether consumption of micronutrient enriched MEC products from 8-14 weeks' gestation to delivery improves birth length in the intervention compared to the placebo group (Phase 1);
- 2) To determine if the daily consumption of micronutrient enriched crackers (MEC) by pregnant mothers from 8-14 weeks' gestation to 5 months post-partum improves attained linear growth of infants at age 5 months and linear growth velocity of infants from birth to age 5 months in the intervention compared to the placebo group (Phase 2).

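### Section 2.4.2 misstates inputs for primary outcomes: the Phase 2 SD unit conflicts with Table 2, 162 fits a birth-length-adjusted model that the SAP does not name, and two Table 2 rows are at 90%, not 80%, power

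*SAP*

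**What the plan says.** All references are to the SAP.

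- **Section 2.4.2, Phase 2.** The aim is "to detect differences in growth velocity of 0.70 cm between the intervention and control groups" at 80% power and significance 0.05, "assuming a standard deviation of 2.2 cm/month, a within-person correlation of 0.73 and a design effect of 1.1 due to village clusters". The result is "a sample size of 162 would be required (81 in each group").
- **Section 2.4.2, Table 2.** Birth length and "Infant length at 5 months (cm") both have an SD of 2.2 cm, a difference to detect of 1.0 cm, a design effect of 1.10 and 114 per group. The footnote covers the whole sample-size column: "Required sample size per group with 80% power and alpha= 0.05".
- **Section 2.4.2, Phase 1.** The same 114 per group for birth length is derived "with power of 0.90, statistical significance of 0.05, and design effect of 1.1".
- **Section 2.4.2, closing paragraph.** After losses the plan expects enough infants for Phase 2, "giving a final sample size of 219-228 to assess Phase 2 outcomes".
- **Section 3.1.** The second goal covers attained length at 5 months and "linear growth velocity of infants from birth to age 5 months".
- **Section 4.2.** The main Phase 2 outcomes are attained length and the gain in length at 5 months. The adjustment variables named, where appropriate, are weight-for-age and breastfeeding practice. Birth length is not among them.

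**The concern.** Velocity from birth to 5 months is a primary outcome, so a reader should be able to tell which quantity was powered, in which unit and under which model.

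The Phase 2 sentence gives an SD per month and a difference in plain centimetres. It lists a correlation without saying which two measurements it links. The number 2.2 also appears in Table 2 as the SD of length itself, which suggests that it was carried across with the wrong unit.

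The model matters because birth length is measured after randomisation and is the Phase 1 primary outcome. Let B be the group difference at birth, C the group difference at 5 months, and b the regression slope of 5-month length on birth length. The simple increment estimates C − B; a model with birth length as covariate estimates C − bB. These agree only if b is 1 or B is zero, and the trial is designed to make B differ from zero. If the sample size assumes one model and the analysis section describes the other, the estimand is left open.

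**Working it through.** **Inputs** (section 2.4.2): difference d = 0.70; SD = 2.2; r = 0.73; design effect 1.1; power 80%; α = 0.05, taken as two-sided because the SAP does not say.

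**Formula**: n per group = 2 × (z for α + z for power)² × SD² × k / d² × 1.1, where k is the factor through which r enters. Ranges run from the normal formula to the noncentral t with the effective sample size n/1.1.

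**1. Reproducing 81 per group**

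With k = 1 and no design effect: 2 × (1.960 + 0.842)² × 4.84 / 0.49 = 155.1.

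| Use of r | k | n per group, with design effect |
|---|---|---|
| Adjusted for an earlier measurement, 1 − r² | 0.467 | 79.7–80.7 |
| Simple change, 2(1 − r) | 0.540 | 92.1–93.2 |
| Mean of two measurements, (1 + r)/2 | 0.865 | 147.5–148.6 |
| 1 − r | 0.270 | 46.1–47.1 |
| r not used | 1 | 170.6–171.6 |

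Only the first row gives the SAP's figure. The t-based 80.7 rounds up to 81. So does the normal formula rounded before the design effect: 155.1 × 0.467 = 72.4, up to 73; 73 × 1.1 = 80.3, up to 81.

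Other routes fail. The simple change without the design effect gives 83.7. A one-sided test gives 72.5 (change) or 62.8 (adjusted). The change form reaches 81 only if r is about 0.76–0.77.

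**2. The unadjusted increment, inputs read as lengths in cm**

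SD of the gain = 2.2 × √(2 × 0.27) = 1.62 cm. The requirement is 93–94 per group, or 186–188 in total.

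| Total N | Power for 0.70 cm, unadjusted increment |
|---|---|
| 162 | 74–75% |
| 186–188 | 80–81% |
| 219 | 86% |
| 228 | 87–88% |

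The birth-length-adjusted form has 80–81% at 162 and about 90–92% at 219–228.

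**3. The SD unit**

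The SD of a difference cannot exceed the sum of the two SDs. With Table 2's values the gain from birth to 5 months has an SD of at most 2.2 + 2.2 = 4.4 cm, or 4.4/5 = 0.88 cm/month, whatever the correlation. If 0.73 is the correlation between the two lengths, it is 1.62 cm, or 1.62/5 = 0.32 cm/month. A velocity SD of 2.2 cm/month is 2.5 times the ceiling (2.2/0.88).

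**4. Power behind Table 2**

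Length rows (SD 2.2, d = 1.0, design effect 1.10):

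- 80% power: 2 × (1.960 + 0.842)² × 4.84 × 1.1 = 83.6 (t-based 84.6), so 84–85 per group.
- 90% power: 2 × (1.960 + 1.282)² × 4.84 × 1.1 = 111.9 (t-based 112.9), so 112–113 per group.
- Power at the stated 114 is 90%.

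The other seven rows reproduce at 80%:

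| Row | Stated | Computed at 80% |
|---|---|---|
| Birth weight | 116 | 114.1–115.1 |
| Haemoglobin | 132 | 133.8–135.3 |
| Breast milk volume | 80 | 77.2–78.3 |
| Breast milk vitamin A | 102 | 99.7–101.1 |
| Maternal dietary vitamin A | 87 | 85.0–86.0 |
| Maternal ferritin | 91 | 90.1–91.2 |
| Infant ferritin | 99 | 97.3–98.3 |

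Their power at the stated n is 79–81%. The footnote is right for seven rows and wrong for two.

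**The case against.** The strongest reply is that 162 is correct. Adjusting for an earlier measurement is a standard use of a within-person correlation, and it returns the SAP's number from the SAP's inputs. Section 4.2 does not exclude birth length. A gain adjusted for birth length also gives the same group contrast as 5-month length adjusted for birth length, so analysing the gain is compatible with 162. This largely stands. A reader might infer that 162 is an arithmetic error; it is not, if birth length is a covariate. What remains is that the SAP names two other Phase 2 covariates and not the one on which the calculation appears to depend.

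A reader might also infer that velocity is badly underpowered, by taking 2.2 cm/month literally with a difference of 0.70 in the same unit and no use of the correlation. The document does not support this. That SD is impossible beside Table 2, and 0.73 is listed as an input.

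It can also be said that section 3.1 supplies the interval for the 0.70 cm. It makes birth to 5 months the natural reading, but the sample-size sentence, whose mean and SD are per month, does not say so.

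Finally, the Table 2 slip errs on the safe side, and the Phase 1 text gives the correct power for birth length. Both are true, and the footnote still contradicts that text.

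**Conclusion.** The point holds as a misstatement of inputs and labels for primary outcomes, not as a shortfall in trial size.

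- **SD unit:** wrong beside Table 2. This needs only Table 2's two SDs and the 5-month interval. That 2.2 was meant as an SD of length in cm is likely but not stated.
- **162:** consistent with adjustment for an earlier length, presumably birth length, which is an inference. For the unadjusted increment it falls short by 12–13 per group (93–94 against 81), with 74–75% power instead of 80%. This assumes that 0.73 is the correlation between birth and 5-month length, that 2.2 cm applies at both ages, that the test is two-sided, and that the covariates named in section 4.2 bring no gain in precision.
- **Table 2:** the two length rows are at 90% power, against a footnote of 80%.

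Phase 1 sets the size of the trial. At the 219–228 infants expected for Phase 2, even the less favourable form has 86–88% power. The correction should be made before unblinding, because the choice of Phase 2 model determines what is estimated.

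**What to change.** 1. In the Phase 2 text, give the SD as 2.2 cm of length at birth and at 5 months, state that 0.73 is the correlation between those lengths, and state 0.70 cm as the difference in gain from birth to 5 months (0.70/5 = 0.14 cm/month). The sponsor must confirm that this is what was meant.
2. Choose one Phase 2 model and make sections 2.4.2 and 4.2 agree:
   - *Unadjusted increment:* increment SD 1.62 cm, requirement 186–188 in total, power 86–88% at the expected 219–228; or
   - *Birth length as covariate:* keep 162, name birth length in section 4.2, and note that it is the post-randomisation Phase 1 outcome, so the adjusted contrast is not the simple increment.
3. Footnote the birth-length and 5-month-length rows of Table 2 as 90% power and leave 80% for the other seven.

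The cost is SAP wording, plus one decision on the Phase 2 model. No additional participants are needed.

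### The sample-size section gives two enrolment totals (308 and 324) and labels the 114-per-group length rows as 80% power when they are 90%

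*SAP*

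**What the plan says.** All of this is in SAP section 2.4.2 and its Table 2.

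- **Phase 1 requirement.** For a 1 cm difference in birth length, "with power of 0.90, statistical significance of 0.05, and design effect of 1.1 due to village clusters", the text concludes that "a minimum sample size of 228 is required (114 in each group").
- **First total.** "we aim to recruit 11 participants from 28 clusters, giving a sample size of 308". The next sentence presents this as making room for stillbirth or prematurity (about 10%, roughly 15 per group) and for drop-out.
- **Second total.** That sentence ends: "drop-out or loss-to-follow-up of approximately 15%, so the total sample size is 324".
- **Retained number.** The Phase 2 count starts from "if 231 participants are retained" and takes off a further 1–5% for infants not breastfed, leaving 219–228.
- **Table 2.** Birth length and infant length at 5 months have identical inputs (SD 2.2, difference 1.0, ICC 0.010, design effect 1.10) and the same result, 114. The footnote to the sample-size column reads "Required sample size per group with 80% power and alpha= 0.05", with no exception for any row. The table is titled as covering secondary outcomes, although sections 3.1 and 4.2 make both lengths main outcomes.

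**The concern.** There are two internal contradictions.

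First, if 308 already contains the allowance for losses, nothing remains to be added, yet 324 is offered as the conclusion of the same sentence. Planned enrolment is among the most basic figures in the design. With two totals it cannot be said whether recruitment met plan, or whether 231 retained is 75% of target (231/308) or 71% (231/324). Section 4.2 commits to the CONSORT extension for cluster trials, so the planned size will have to be reported and compared with what was achieved.

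Second, identical inputs cannot require 114 per group at both 90% power (Phase 1 text) and 80% power (Table 2 footnote). For birth length the reader at least has the text to set against the footnote. For attained length at 5 months there is no such text, because the Phase 2 paragraph powers growth velocity only. A reader relying on the footnote would see 219–228 infants against an apparent 80% requirement of 228 and conclude that a primary outcome falls at or below 80% power.

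**Working it through.** **Inputs** (all from SAP section 2.4.2 and Table 2): difference 1.0 cm; SD 2.2 cm; ICC 0.010; average cluster size 11; alpha 0.05; 28 villages; losses of about 10% and 15%; a further 1–5% not breastfed. The SAP does not say whether alpha is one- or two-sided. Two-sided is assumed; one-sided gives 66 (80% power) or 92 (90%) per group, neither of which is 114.

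**1. Reproducing 114 per group**

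Design effect = 1 + (11 − 1) x 0.010 = 1.10.

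n per group = 2 x [(z for alpha + z for power) x SD / difference]² x design effect.

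| Power | Unclustered n (normal) | x 1.10 | Rounded up first, then x 1.10 | t-based n, then x 1.10 |
|---|---|---|---|---|
| 90% | 101.71 | 111.9 | 102 x 1.10 → 113 | 103 x 1.10 → **114** |
| 80% | 75.98 | 83.6 | 76 x 1.10 → 84 | 77 x 1.10 → 85 |

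The SAP's 114 is reproduced exactly at 90% power and cannot be obtained at 80%.

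**2. Is the footnote right for the other rows?**

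Same formula, normal approximation, rounded up before and after the design effect:

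| Table 2 row | SAP | At 80% | At 90% |
|---|---|---|---|
| Birth weight | 116 | 115 | 153 |
| Haemoglobin | 132 | 135 | 181 |
| Breast milk volume | 80 | 79 | 104 |
| Breast milk vitamin A | 102 | 101 | 135 |
| Maternal dietary vitamin A | 87 | 86 | 115 |
| Maternal ferritin | 91 | 91 | 122 |
| Infant ferritin | 99 | 98 | 131 |

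These seven rows fit 80% closely and are far from 90%. The footnote is wrong for the two length rows only.

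**3. Power for length at the expected numbers**

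Effective n per group = n / 1.10.

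| Analysed (per group) | Effective n | Power, t with individual-level df | Power, t with 28 − 2 = 26 village-level df |
|---|---|---|---|
| 228 (114) | 103.6 | 0.903 | 0.88 |
| 219 (109.5) | 99.5 | 0.891 | 0.87 |

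**4. The enrolment chain from 308**

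- 28 x 11 = 308.
- 10% of 308, per group: 30.8 / 2 = 15.4, matching the SAP's roughly 15.
- 308 x (1 − 0.10 − 0.15) = 308 x 0.75 = 231, matching exactly.
- 231 x 0.95 = 219.5 and 231 x 0.99 = 228.7, matching 219–228 apart from rounding down.

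**5. The same chain from 324**

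- 324 / 28 = 11.57 per village, not 11.
- 324 x 0.75 = 243 (or 324 x 0.90 x 0.85 = 248 if the losses are multiplied), not 231.
- 243 x 0.95 = 230.9 and 243 x 0.99 = 240.6, so 231–241, not 219–228.

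**6. Where 324 might come from**

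- Inflating the required 228: 228 / 0.75 = 304, or 228 / (0.90 x 0.85) = 298.04, rounded up to 299. Neither is 324.
- 308 x 1.05 = 323.4 is close, but the SAP states no 5% rate for this step.
- Inflating the 22-village figure: 22 x 11 = 242, or 121 per group; 121 / 0.75 = 161.3, rounded up to 162, and 2 x 162 = 324. This is a possible origin, but the SAP does not state it, and on that route 308 would fall short of the target rather than already allowing for losses.

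**The case against.** The strongest reply is that both slips are clerical and change no design conclusion. The operative recruitment statement is explicit (28 villages, 11 women each), the Table 2 design effects use a cluster size of 11, and every later count follows from 308, so 324 is a single stray figure. Either total retains enough: 231 or 243 against 228 for Phase 1 and 162 for growth velocity. The mislabelled power errs on the cautious side, and no analysis depends on the footnote. The top of the 219–228 range also equals 228, so even a reader misled by the footnote would see only a small shortfall.

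Most of that stands, and it limits the consequence: this point does not show an underpowered trial. It is also fair that a power of 0.90 should not be stated too firmly, since village-level degrees of freedom bring it to about 0.87–0.88. A further caution is fair too. The 231 removes premature births, whereas section 2.4.1 keeps premature infants in the growth measurements and section 4.2 analyses live-born infants by intention to treat. Restoring consistency with 231 does not make it the final analysis count.

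The reply does not remove the errors. A stated total and a stated power are wrong as written, and the wrong power is the only one given for a primary outcome.

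**Conclusion.** Both parts hold. Section 2.4.2 states two totals that differ by 16 women (5%). The SAP's own figures (11 per village, about 15 exclusions per group, 231 retained, 219–228 in Phase 2) support 308 and not 324, which would retain 243. The 80% label in Table 2 is wrong for birth length and 5-month length: 114 per group is the 90% requirement, and 80% would need 84–85. At 219–228 analysed, power for a 1 cm difference is nominally 0.89–0.90, or about 0.87–0.88 with 26 village-level degrees of freedom.

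These figures assume two-sided alpha, the SAP's SD of 2.2 and design effect of 1.10, and additive losses, which is the reading that reproduces 231. The consequence is an ambiguous enrolment target and an understated power for a primary outcome, not an inadequate sample. It should be corrected.

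**What to change.** 1. State one total. If it is 308 (28 villages x 11), keep 231 retained after 25% loss and 219–228 for Phase 2, and delete 324. If 324 is the intended target, say how it was derived, restate the recruitment as an average of 11.6 per village, and carry 243 retained and 231–241 for Phase 2 through the paragraph.
2. In Table 2, mark birth length and infant length at 5 months as 90% power and leave the 80% footnote for the other rows.
3. Label those two rows as primary outcomes and amend the table title, which now refers to secondary outcomes only.

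The cost is SAP wording only. No change to design, data collection or analysis follows.
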